4.3 General Statistical Considerations

Confidence intervals (CIs) around geometric mean ratios will have 90% coverage probability; all other CIs will have 95% coverage. Hypothesis tests will have test size of 5%. No adjustments will be made for multiple comparisons. The justification for no such adjustment is as follows. Rationale for multiple comparisons generally emphasizes control of a family-wise error rate when there is a global null hypothesis. For example, in a multiple-arm clinical trial comparing different drugs to a placebo, a global null hypothesis would be of the form “at least one of the active arms performs better than the placebo” (Parker and Weir, 2020). The emphasis in A5372 is on estimation (CIs) not hypothesis testing (p-values). Furthermore, within an arm, PK micro parameters are jointly estimated through modeling, and descriptive summaries of PK parameters are not independent (participants with low C_{min} values are expected to have a low AUC values). Therefore it would be incorrect to adjust as if these are independent estimands. The same rationale holds across arms: the null hypothesis is not that at least one of the two doses is effective but to estimate PK parameters based on all available data.

4.4 PK Parameter Calculations (Conducted by Study Chair and Study Pharmacologist)

In separate final analyses for Arms 1 and 2, DTG plasma PK parameters (primary outcomes) will be determined for evaluable participants (the primary analysis population) using nonlinear mixed-effects population PK modeling. Participant-specific C_{min} values will be estimated both from the model and as the observed minimum plasma concentration.

4.5 Interim Analysis of DTG PK Data to Determine Decision for Opening Arm 2

Prior to opening Arm 2, when DTG drug concentrations are available for at least 32 evaluable participants from Arm 1, an interim analysis of DTG PK data will be conducted by the pharmacologist. Results will be reviewed by the core team. Arm 2 will open to enrollment if simulations based on Arm 1 PK data support the hypothesis that 50 mg DTG dosed QD in combination with 1HP will result in DTG trough concentrations that mimic reported plasma concentrations following a 10 mg DTG QD dose without RPT.

There will not be a formal SMC review to evaluate the interim DTG PK data; however, the SMC will be notified of the decision as soon as the PK interim review by the core team is completed.

Background. In the SPRING-1 study, a 10 mg daily dose of DTG was associated with virologic suppression [18] and, as such, the DTG PK parameters achieved for this dose in SPRING-1 are considered adequate targets. The 5th, 50th, and 95th percentiles for this dose were 158, 316, and 555 ng/mL, respectively.

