10.4 Sample Size and Accrual

Sample size estimates are aimed to provide data to support precise estimation of the pharmacokinetic model parameters for DTG in the presence and absence of 1HP. These models, once validated, will further be used to deliver dosing algorithms for DTG to be recommended for treatment of patients living with HIV and co-infected with LTBI, pending appropriate safety assessment.

The sample size assessment was done by evaluating different study designs (varying number of participants and time points) using clinical trial simulations. The stochastic simulation-estimation (SSE) methodology for clinical trial simulation and re-estimation was employed to evaluate sample sizes required to evaluate key pharmacokinetic parameters with precision adequate for decision making on use of RPT + DTG at the proposed doses. This methodology simulates the data from the planned trial with proposed design (number of samples, participants) followed by the estimation of the parameters under the true and alternative models. This is repeated at least 1000 times and parameter estimates relative standard errors and between subject variability (BSV) estimates are assessed. This methodology was used to assess sample size calculations and probability of opening Arm 2. The effect of RPT on DTG PK parameters

(bioavailability) was assumed to be 30%-50% decrease based on a previously developed model of DTG + 3HP [16]. The range of inter-participant variability in PK parameters (CL and F) was assumed to be 25-40%. The team has assumed design where each participant is its own control and time course of RPT induction is considered. Under these assumptions, data from ≥ 32 participants will provide $>80\%$ power to detect the DDI effect on bioavailability and to unbiasedly (relative bias $<5\%$) and precisely (RSE $<25\%$) estimate PK parameters and inter-participant variability. These unbiased parameters will be then used for simulations of Arm 2 and derivation of the median 5th percentile of DTG troughs by simulations. Probability of opening Arm 2 will be dependent on magnitude of both, decrease in bioavailability due to DDI and between participant variability. Decrease in bioavailability of up to 35% coupled with acceptable inter-participant variability (up to 30%) will provide 90% chance of satisfying criteria for opening Arm 2.

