10.6 Analyses

Primary outcome plasma PK parameters (C_{min} , AUC_{0-24h} , and C_{max}) will be determined using **nonlinear mixed-effects population pharmacokinetic modeling**. PK parameters will be log-transformed as needed.

Primary PK analysis:

The bootstrap method with replacement will be applied on the observed C_{trough} values from Arm 1, and the mean and 95% CI of the 5th percentile C_{trough} will be calculated. The **lower bound of a 95% CI around the 5th percentile of C_{min}** from Arm 1 will be compared with the 5th percentile of C_{tau} in the DTG 10 mg dosing arm (i.e., 158 ng/mL) from the SPRING-1 study, which has been demonstrated to be sufficient in maintaining viral suppression. If the **lower bound of the 95% CI around the 5th percentile C_{min}** is greater than 158 ng/mL, the dosing is considered acceptable. The same analysis will be conducted for Arm 2 if it opens.

Geometric mean ratios and associated 90% confidence intervals within arm will be calculated to assess the overall effect of 1HP on DTG PK.

For all PK parameters (including both primary and other outcome PK measures), descriptive statistics including mean, standard deviation, median, interquartile range, minimum, and maximum will be presented. All statistical tests will be performed without adjustment for multiple comparisons unless otherwise stated.

Detailed analysis methods will be put in a Statistical Analysis Plan.

Because PK variability has been associated with differences in drug response, understanding whether differences in DTG and RPT concentrations observed in A5372 have a genetic basis will be explored as an exploratory objective. Polymorphisms in host genes involved in both DTG and RPT metabolism or transport will be explored. The primary genes of interest will include: CYP3A4/5, UGT1A1, PXR (pregnane x receptor), CAR (constitutive androstane receptor), as well as other metabolic enzymes and transporters that may play a role in either DTG or RPT disposition (TBD).

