3.1 Primary Outcome Measures

The primary outcome measures are participant-specific estimates of the day 0 and day 28 plasma DTG PK parameters C_{max} , C_{min} , and area under the concentration-time curve over 24 hours (AUC_{0-24h}) while on the Arm 1 regimen and, if Arm 2 opens, the Arm 2 regimen. [Outcome Measure 10.2.1.1].

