6.4 GMR, Within-subject Design

In the within-subjects design, PK parameters are estimated for an individual participant under both conditions of interest. For the individual participant i , PK parameter differences on the log scale Y_i are calculated: $Y_i = \log(X_i^B) - \log(X_i^A)$, where X_i^B and X_i^A are untransformed PK parameters for participant i for conditions B and A, respectively. The sample mean and sample standard deviation of the Y_i are calculated. With \bar{Y} and s defined as the sample mean and sample standard deviation of the within-participant differences on the log scale (Equations [2] and [3]), the GMR is estimated by exponentiating [2] and the corresponding CI is given by exponentiating the endpoints of [1].

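### The 90% interval for the primary geometric mean ratios is too narrow if its inputs are shrunken individual estimates from the population PK model, which is the natural reading of SAP 4.4

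*SAP*

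**What the plan says.** SAP 3.1 defines the outcome: "The primary outcome measures are participant-specific estimates of the day 0 and day 28 plasma DTG PK parameters" (Cmax, Cmin and AUC0-24h). SAP 4.4 gives the source: these parameters "will be determined for evaluable participants (the primary analysis population) using nonlinear mixed-effects population PK modeling". Protocol 10.6 likewise names "nonlinear mixed-effects population pharmacokinetic modeling" for all three. SAP 4.3 adds that, within an arm, the parameters are estimated jointly through the model.

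For inference, protocol 10.6 states: "Geometric mean ratios and associated 90% confidence intervals within arm will be calculated to assess the overall effect of 1HP on DTG PK". SAP 6.4 gives the formula. Each participant's two values are log-transformed and differenced, "The sample mean and sample standard deviation of the Y_i are calculated", and a t-interval with n-1 degrees of freedom is exponentiated. SAP 4.3 states the coverage: "Confidence intervals (CIs) around geometric mean ratios will have 90% coverage probability". SAP 4.8.2 makes this ratio and interval the primary inference for Objectives 2 and 3, and its estimand table plans no sensitivity or supplementary analysis.

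Two places point another way. SAP 1.3 defines Cmax and Cmin as observed concentrations. SAP 4.7 describes AUC0-24h as estimated from the concentrations collected, with the two twice-daily intervals summed for Arm 1 on Day 28. SAP 4.4 also plans two versions of Cmin, one from the model and one observed, and does not say which enters the ratio.

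**The concern.** The SAP 6.4 formula suits values computed separately from each participant's measured profile at each visit. Their sample SD then contains both the true variation in the interaction and the measurement error.

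Participant-specific values from a mixed-effects model are ordinarily empirical Bayes estimates. Each is a compromise between the participant's own data and the population value, and the two visits can share the same random effects. Both features shrink the SD of the within-participant differences. The formula has no term for this or for the uncertainty of the fitted model, so the interval claims more precision than the data give. With no sensitivity analysis planned, nothing else in the report would expose this. Two analysts following the plan could publish quite different intervals from the same concentrations.

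**Working it through.** **Inputs from the documents.** Nominal coverage is 90% (SAP 4.3). There are at least 32 evaluable participants (SAP 2.4), hence 31 degrees of freedom and t(0.95, 31) = 1.6955. Each intensive visit has 10 samples in Arm 1 and 8 in Arm 2, with a minimum of 6 (protocol 6.3.11). The planning model lowers bioavailability F by 30-50% and varies CL and F between participants (protocol 10.4: "The range of inter-participant variability in PK parameters (CL and F) was assumed to be 25-40" per cent). The random effects named there and in SAP 2.4 are between-subject only.

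**Step 1: the plan's own figure.** The interval is exp(mean ± 1.6955 × s/√32). On unshrunken per-visit values, 200,000 simulated trials gave coverage of 0.900. The stated 90% is reproduced.

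**Step 2: shrinkage in closed form.** In a balanced log-scale mixed model, the mean of the individual estimates is unchanged, but the SD of their differences is multiplied by λ = w²/(w² + σ²/m). Here w is the visit-level SD, σ the residual SD and m the number of samples. Coverage becomes P(|t31| < λ × 1.6955):

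| λ | 1 | 0.9 | 0.8 | 0.7 | 0.5 | 0 |
|---|---|---|---|---|---|---|
| Coverage | 0.900 | 0.863 | 0.815 | 0.756 | 0.597 | 0 |

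Examples with assumed w and σ:
- w = 0.2, σ = 0.2, m = 10: λ = 0.04/(0.04 + 0.004) = 0.909, coverage 0.867.
- Same, m = 6: λ = 0.04/(0.04 + 0.00667) = 0.857, coverage 0.844.
- w = 0.1, σ = 0.3, m = 6: λ = 0.01/(0.01 + 0.015) = 0.40, coverage 0.497.

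**Step 3: population PK simulation.** I used a one-compartment steady-state model with individual (MAP) estimates, n = 32, the protocol's intensive sampling times and 200 trials per setting (Monte Carlo error about ±0.03). The assumptions not in the documents are CL/F 1 L/h, V/F 17 L, ka 1.5/h, between-subject SDs 0.3/0.2/0.5, and a true F ratio of 0.65. The model's once-daily trough is 986 ng/mL, against the 1003 in protocol 2.1.1 (printed there as ug/mL, read here as ng/mL). Coverage of the nominal 90% interval was:

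| Interaction SD / residual error (assumed) | Arm 1 AUC / Cmax / Cmin | Arm 2, all three |
|---|---|---|
| 0.3 / 20% | 0.855 / 0.835 / 0.885 | 0.815 |
| 0.2 / 20% | 0.835 / 0.805 / 0.860 | 0.770 |
| 0.1 / 20% | 0.580 / 0.695 / 0.815 | 0.495 |
| 0.2 / 40% | 0.585 / 0.605 / 0.710 | 0.505 |
| 0.2 / 40%, six samples | 0.435 / 0.455 / 0.610 | not run |
| 0.2 / 20%, no interaction random effect in the model | 0 / 0.41 / 0.71 | 0 |

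**Step 4: why the last row reaches zero.** Suppose the interaction multiplies F by one common factor θ and nothing else changes between visits. Then AUC is F_i × dose/CL_i on Day 0 and θ × F_i × dose′/CL_i on Day 28. The ratio is θ × dose′/dose for every participant, so s = 0. With θ between 0.5 and 0.7, that constant is 1.0 to 1.4 in Arm 1 (daily dose 100 against 50 mg) and 0.5 to 0.7 in Arm 2. In Arm 2 the whole curve scales by θ, so Cmax and Cmin collapse too. In Arm 1 the change from once to twice daily makes the Cmax and Cmin ratios depend on individual parameters, so those intervals are too narrow but not of zero width.

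**The case against.** The documents never say that post hoc estimates are used, and they do not fix the random-effects structure. CL and F variability comes from the sample-size simulation; the final model is still to be developed, and nothing excludes inter-occasion or interaction variability. A reader might infer that the interval will collapse to a point. The documents do not support that: zero width needs the restricted model, and in Arm 1, the only arm certain to run, it would arise for AUC alone.

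A reader might also infer that Cmax has only a model-based source. SAP 1.3 defines it as an observed maximum, and SAP 4.7 can be read as a per-profile AUC. On that reading all three parameters have per-visit values and the formula keeps its 90%. This stands, and it means false precision is not inevitable. It does not settle the matter, because SAP 4.4 and protocol 10.6 name the model explicitly and nothing says which reading governs.

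The coverage figures depend on assumed variances. Arm 1's ten samples limit the loss, and the sparse troughs on Days 3, 14 and 21 could reduce shrinkage somewhat. This is fair: the loss may be moderate.

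Finally, no decision turns on this interval. SAP 6.5 sets no equivalence limits, and SAP 4.3 puts the emphasis on estimation. That limits the consequence, but the interval is still the stated primary inference.

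**Conclusion.** The point holds conditionally. If individual model estimates enter SAP 6.4, the interval does not deliver the 90% coverage stated in SAP 4.3. Under moderate assumptions (interaction variability 20-30%, residual error 20%) coverage is about 0.77 to 0.89. With 10% interaction variability or 40% residual error it is about 0.44 to 0.82. It under-covered in every setting tested. These sizes rest on PK values and variances that the documents do not give; the direction follows from shrinkage. If per-visit values are used, the formula is sound. The plan supports both readings and so needs a decision.

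A reader might extend this to the comparison of the 5th percentile with 158 ng/mL. The documents do not support that for the protocol's bootstrap, which resamples observed C_trough (protocol 10.6 then writes Cmin without giving its source). The preliminary interim review in SAP 4.5.1 also uses observed minimum concentrations, and Arm 2 opens on a simulation criterion (SAP 4.5.2). What is at stake is the reported precision of the interaction estimate.

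**What to change.** In SAP 4.4, 4.7 and 6.4, state that the ratios use per-visit values from each participant's measured profile: observed Cmax, observed Cmin and non-compartmental AUC0-24h. Say explicitly that the observed Cmin enters the ratio. Align protocol 10.6, since changing the SAP alone would put the two documents in conflict. Keep the population model for Objective 1 and for the Arm 2 simulations.

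If model-based ratios are kept, take their interval from the model, by a participant-level bootstrap with refitting or from the parameter covariance. State the visit-level and interaction random effects, and report shrinkage. Do not apply the t-interval to individual estimates. The estimand table's reference to Section 8 for the ratio method should also be corrected to Section 6.

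The cost is wording in both documents and one routine non-compartmental run on concentrations already planned. The drawback is sampling density: Arm 1's second dosing interval has samples only at 12, 13, 14, 23 and 24 hours, and a participant with the minimum of six may not yield a reliable AUC. For those, the model-based interval would serve as a supplement.

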4.5.1 Preliminary Interim Analysis (Conducted by Study Statisticians)

Initially, when DTG concentrations from the first 32 evaluable participants (ie, participants in the primary PK analysis population) in Arm 1 are available, the core team will review the DTG PK data to ensure sufficient plasma exposures of DTG (C_{tau}) are achieved with twice-daily DTG dosing. This review will consist of summaries of data completeness, participant evaluability for PK, and observed minimum concentrations. If: (1) there are at least 32 evaluable participants with minimum concentrations, (2) no more than 5% of these participants exhibit minimum DTG concentrations above 158 ng/mL, and (3) there are no worrisome outliers among these minimum concentrations, the PK data will be used to model the anticipated PK of QD DTG when coadministered with 1HP, as described in Section 4.5.2. Based on model simulations of QD DTG dosing with 1HP, a decision will be made on whether to open Arm 2 for enrollment. Details on the criteria for opening Arm 2 are given in the protocol (Section 7.4) and above (beginning of Section 4.5).

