For all SMC reviews, the SMC will be provided detailed information on safety (including treatment tolerability and mortality), and administrative aspects (including accrual, retention, compliance with study requirements).

An interim review of DTG PK data will be conducted by the CMC team and the SMC once DTG PK data from participants in Arm 1 (n=32 evaluable) are available prior to opening Arm 2.

A 10 mg daily dose of DTG was associated with virologic suppression in the SPRING-1 study [18] and the pharmacokinetic parameters reached following this dose in SPRING-1 are adequate to be considered as DTG C_{trough} PK targets (5th, 50th, and 95th percentile of 158, 316, and 555 ng/mL, respectively). These PK data form the basis for opening rules for Arm 2. Once DTG C_{trough} PK data are available from 36 participants in Arm 1, an evaluation of DTG PK in these participants will occur.

Arm 2 will open to enrollment if simulation of Arm 1 PK data suggest that 50 mg DTG dosed QD in combination with 1HP will result in DTG trough concentrations that mimic reported plasma concentrations following a 10 mg DTG QD dose. Based on the population pharmacokinetic model built and adequately evaluated based on the data from Arm 1, we will simulate the clinical trial population of Arm 2 (QD dosing) 1000 times, and generate troughs for each of these simulated participants. These trough values will be summarized in terms of reported statistics from the SPRING Study (5th, 50th, and 95th percentile for each repetition). The median value (from 1000 repetitions) of the 5th percentile of DTG trough concentrations (C_{tau}) assessed via simulations should not fall below the reported 5th percentile of 158 ng/mL which was observed in the 10 mg DTG dose from the SPRING-1 study. If this criterion is met, A5372 will open Arm 2 for enrollment for evaluation of QD DTG 50 mg given with 1HP. The estimation of expected lower boundary with QD dosing (derived from simulations) will be done using model-based analysis with the models derived from PK data collected data in Arm 1 receiving 50 mg BID + 1HP.

Detailed plans for study monitoring will be outlined in a Study Progress Data Safety Monitoring Plan developed by the Statistical and Data Management Center (SDMC) prior to enrollment of the first participant.

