2.1 Overview of Study Design

A5372 is an open-label, non-randomized, two-arm, multicenter PK study to investigate the potential interactions between DTG and steady state RPT when RPT is prescribed with INH daily for 4 weeks (1HP) in HIV-1 and LTBI co-infected individuals.

The study regimen will be as follows, days 1 through 28.

Arm 1

- DTG 50 mg orally BID (~12 hours apart)
 - 1st dose: DTG 50 mg each morning from non-study ARV supply
 - 2nd dose: DTG 50 mg each evening from study supply
- 1HP: INH 300 mg + RPT 600 mg orally each morning for 4 weeks

Arm 2 (upon opening; contingent on assessment of DTG PK data from participants in Arm 1)

- DTG 50 mg orally each morning from non-study ARV supply
- 1HP: INH 300 mg + RPT 600 mg orally each morning for 4 weeks

All participants must also be on once-daily DTG-based ARV treatment with 2 NRTIs (excluding TAF) during the study. All participants must receive pyridoxine (vitamin B6) 25 or 50 mg with each dose of INH based on the current local, national, or international dosing guidelines.

Initially, the study will open with Arm 1. Once DTG concentrations data from the first 32 evaluable participants in Arm 1 are available, the core team will review the DTG PK data to ensure sufficient plasma exposures of DTG (C_{tau}) are achieved with twice-daily DTG dosing. This review will consist summarizing data completeness, participant evaluability for PK, and observed minimum concentrations. Provided: (1) there are 32 evaluable participants with minimum concentrations, (2) these minimum concentrations are above 158 ng/mL, and (3) there are no worrisome outliers among these minimum concentrations, the PK data will be used to model the anticipated PK of QD DTG when coadministered with 1HP. Based on these models and simulations of QD DTG dosing with 1HP, a decision will be made on whether to open Arm 2 for enrollment. Details on the criteria for opening Arm 2 are given in the protocol (Section 7.4) and herein (Section 4.5).

Plasma PK profiles for DTG will be determined at two time points. At the first time point, plasma samples will be drawn in participants at steady state with respect to DTG when receiving once daily DTG prior to 1HP. At the second time point, DTG will be given BID in Arm 1 and QD in Arm 2 during the 1HP LTBI regimen; PK sampling for DTG will occur on day 28 of the 1HP regimen.

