2.2 Hypothesis

Dolutegravir (DTG) concentrations, when given twice daily (BID) or once daily (QD) with coadministration of 4 weeks daily rifapentine (RPT) (600 mg) and isoniazid (INH) (300 mg) [1HP], will maintain steady-state plasma trough DTG concentrations above 158 ng/mL in 95% of study participants. The value 158 ng/mL is the 5th percentile steady-state trough concentrations of DTG which has been demonstrated to be sufficient in maintaining virologic suppression.

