2.6 Interim Core Team Reviews

The core team will meet regularly to review safety data. Details can be found in the A5372 SPDSMP.

In addition, when DTG PK data from the first 32 evaluable participants in Arm 1 are available, an interim analysis of Arm 1 DTG PK data will be conducted by protocol pharmacologist and reviewed by the core team. The main purpose of this review is to determine whether Arm 2 should open, or the study should proceed with Arm 1 only. This analysis is described in Section 4.5 herein.

There will not be a formal SMC review to evaluate the interim DTG PK data; however, the SMC will be notified of the decision as soon as the PK interim review by the core team is completed.

3 Outcome measures

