4.5.2 Model-based Interim Analysis (Conducted by Study Pharmacologist)

Criterion for opening Arm 2. In addition to the three criteria above, when DTG concentrations from at least 32 evaluable participants (ie, participants in the primary PK analysis population) in Arm 1 are available, a model-based evaluation of DTG PK in these BID participants will occur. The study pharmacologist will develop a nonlinear mixed-effects population pharmacokinetic model, based on available concentrations from all Arm 1 participants (ie, participants in the secondary PK analysis population). From the developed and evaluated model, concentrations for 100 hypothetical participants will be simulated for Arm 2/QD dosing of DTG 1000 times. The parameter of primary interest is C_{24} , the expected DTG concentration at the end of the 24h dosing interval at steady state. For each simulated trial, the 5th, 50th, and 95th percentile of DTG trough concentrations, C_{24} , will be determined.

Of the 1000 simulated trials, the median value of the 5th percentile of DTG C_{24} will be compared to 158 ng/mL, which is the 5th percentile of DTG C_{24} observed for the 10 mg daily DTG dose in SPRING-1. If the median C_{24} value among simulated 5th percentiles is at or above 158 ng/mL, A5372 Arm 2 will open for enrollment, for evaluation of DTG 50 mg QD dosing with 1HP.

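### SAP 4.5.1 reverses its own go/no-go criterion: adequate twice-daily DTG minima would fail the check that must be passed before Arm 2 is modelled

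*SAP*

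**What the plan says.** SAP 4.5.1 describes a preliminary interim review of Arm 1 by the core team. Its stated purpose is "to ensure sufficient plasma exposures of DTG (C_{tau}) are achieved with twice-daily DTG dosing". The data go forward to once-daily modelling if three conditions hold: at least 32 evaluable participants with minimum concentrations, that "no more than 5% of these participants exhibit minimum DTG concentrations above 158 ng/mL", and no worrisome outliers.

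SAP 2.1 sets out the same three conditions, introduced as a proviso, but gives the second as "2) these minimum concentrations are above 158 ng/mL", with no percentage. SAP 2.2 states the hypothesis that DTG given with 1HP "will maintain steady-state plasma trough DTG concentrations above 158 ng/mL in 95% of study participants".

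SAP 4.5.2 then adds the simulation criterion. It opens with "In addition to the three criteria above", so the three conditions also bind on the opening of Arm 2. Its own rule is that, if the median "among simulated 5th percentiles is at or above 158 ng/mL, A5372 Arm 2 will open for enrollment". Protocol 7.4 has the same simulation rule: the median simulated 5th percentile "should not fall below the reported 5th percentile of 158 ng/mL". Protocol 10.6 accepts a dosing when the lower confidence bound for the 5th percentile exceeds 158 ng/mL. SAP 2.6 gives the purpose of the interim PK review as being to "determine whether Arm 2 should open, or the study should proceed with Arm 1 only".

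**The concern.** A review meant to confirm sufficient exposure is written so that sufficient exposure fails it. If all 32 minima exceed 158 ng/mL, the share above is 100% and the condition is not met. It is met only when at least 31 of 32 are at or below 158.

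This is a pre-specified decision rule. Neither protocol 3.0 nor protocol 7.4 puts a number on the check of twice-daily exposure, so the SAP is the only place where it is quantified. Followed literally, good Arm 1 data would prevent the once-daily modelling and the study would continue with Arm 1 only.

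If the slip is instead repaired informally at the interim, the team must decide how many participants may fall below 158, and SAP 2.1 and a direction-corrected 4.5.1 give different answers. That choice would be made in an open-label study with the Arm 1 concentrations in hand. Under SAP 2.6 and 4.5 there is no formal SMC review of those data, only notification of the decision.

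**Working it through.** **Inputs from the documents.** Threshold 158 ng/mL and a 5% limit (SAP 4.5.1); at least 32 evaluable participants (SAP 4.5.1); 36 enrolled per arm (SAP 2.4); target of 95% of participants above 158 (SAP 2.2, protocol 1.1).

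**The plan's own figure.** SAP 2.4 describes 36 per arm as about 12% more than 32. 36/32 − 1 = 12.5%, so this reproduces, and the check would be run on 32 to 36 participants. The power and Arm 2 opening probabilities in protocol 10.4 come from a population PK simulation whose full parameters are not given. They cannot be reproduced and are not needed here.

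**The 5% limit as a count.** 0.05 × 32 = 1.6 and 0.05 × 36 = 1.8, so the limit is 1 participant at either size (1/32 = 3.1%, 2/32 = 6.25%; 1/36 = 2.8%, 2/36 = 5.6%).

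**Direction, side by side.** Above or not below 158 is acceptable in SAP 2.1, 2.2 and 4.5.2 and in protocol 1.1, 2.1.1, 7.4 and 10.6. Above 158 counts against the arm only in SAP 4.5.1. The written rule is also practically incompatible with 4.5.2: twice-daily minima almost all at or below 158 would have to yield a simulated once-daily 5th percentile of at least 158.

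**Rule as written.** With independent participants and true share p above 158, P(pass) = (1 − p)^n + n·p·(1 − p)^(n − 1). At n = 32:

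- p = 0.95 (the hypothesis): 1.4e-39
- p = 0.50: 33/2^32 = 7.7e-9
- p = 0.10: 0.156
- p = 0.05: 0.520

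The chance of passing rises as exposure worsens.

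**Direction corrected, two tolerances.** With true share q below 158, P(at most 1 below) = (1 − q)^n + n·q·(1 − q)^(n − 1), and P(none below) = (1 − q)^n. For q = 0.05 and n = 32: 0.95^32 = 0.194; 32 × 0.05 × 0.95^31 = 0.326; sum 0.520. The value q = 5% is the boundary of the hypothesis; 2% and 1% are assumed values that the documents do not give.

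| q | n | At most 1 below | None below |
|---|---|---|---|
| 5% | 32 | 0.520 | 0.194 |
| 2% | 32 | 0.866 | 0.524 |
| 1% | 32 | 0.959 | 0.725 |
| 5% | 36 | 0.457 | 0.158 |
| 2% | 36 | 0.838 | 0.483 |
| 1% | 36 | 0.950 | 0.696 |

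The two rules disagree whenever exactly one participant is below 158.

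**The case against.** The strongest reply is that this is an evident wording slip that nobody would apply. SAP 2.1 gives the same condition in the right direction, as does every other use of the threshold. Protocol 7.4 also treats the simulation criterion as enough to open Arm 2, so a literal SAP condition that blocked it would conflict with the protocol. This stands as far as intent goes: the direction can be recovered, and literal execution is unlikely. It does not remove the error. The SAP allows the modelling only after the three conditions are met, and protocol 3.0 likewise puts a review of twice-daily exposure before the modelling.

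The second reply is that the tolerance is not really open. SAP 2.1 is an overview that refers to 4.5 for detail, and the only stated figure, 5%, sits in the operative section and matches the 95% hypothesis. This has weight and makes the tolerance the lesser point. SAP 2.1 nevertheless states the condition without any allowance.

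The third reply is that the two tolerances would seldom differ in practice. Protocol 2.1.1 reports a median trough of 1,123 ng/mL with twice-daily DTG and rifampin in 10 participants, and CVs of 62% and 71% for DTG alone. Assuming log-normality, σ = √ln(1 + CV²) = 0.57 to 0.64 and ln(1123/158) = 1.96, which puts about 0.03% to 0.1% below 158. At n = 32, at most 1 below then passes with probability above 0.999 and none below with 0.97 to 0.99. With an assumed CV of 100% the figures are 0.96 and 0.74. That is a fair reading, but it borrows from a different rifamycin; protocol 2.1.1 says there are no PK data for DTG with daily rifapentine.

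**Conclusion.** The concern holds. Criterion (2) in SAP 4.5.1 is reversed and must be corrected, because it is a binding step in the decision on Arm 2. As written, it is almost impossible to pass when exposure is adequate (about 1.4e-39 at n = 32 if 95% are truly above 158) and passes about half the time (0.52) when only 5% are above. The harm is confined to wrongly stopping at Arm 1, since SAP 4.5.2 separately guards against opening an under-exposed once-daily arm.

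The difference in tolerance between SAP 2.1 and 4.5.1 is secondary but real. Its size depends on the unknown share below 158: large near 5%, small if twice-daily troughs resemble those reported with rifampin. The probabilities assume independent participants and a common true share.

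**What to change.** 1. In SAP 4.5.1, criterion (2), replace above with below, so that no more than 5% of participants may have minima below 158 ng/mL. This is the direction the hypothesis requires. A value of exactly 158 then counts as acceptable, in line with SAP 4.5.2 and protocol 7.4.
2. Reword SAP 2.1 so that it states the same condition and the same tolerance.
3. State the tolerance as a count for the number analysed. The 5% rule allows 1 at any n from 32 to 36. Section 4.5.1 should also say whether the check uses the first 32 evaluable participants or all those available, since it refers both to the first 32 and to at least 32.
4. Fix these points before Arm 1 data are reviewed. If the review has already taken place, record which rule was applied.

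If the sponsor prefers a tolerance other than 5%, it should choose knowing the failure rates: at n = 32 with exactly 5% truly below 158, at most 1 fails 48% of the time and none fails 81%.

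The cost is one word and a stated count in 4.5.1 and one aligned sentence in 2.1, with no extra data or participants. The tolerance chosen does alter the chance that the modelling proceeds.
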